3.2.3 Additional endpoints supporting primary and key secondary endpoints

3.2.3.1 Other annualised exacerbation rates

To assess the effect of tezepelumab on other endpoints associated with asthma exacerbations, an annualised rate of exacerbations associated with emergency room visit or hospitalisation will be chosen as a secondary endpoint (a subset of the primary endpoint defined in [Section 3.2.1.1](#), specifically the 2nd and 3rd bullets only).

Note that the primary endpoint does not consider adjudicated outcomes at all in the definition given in [Section 3.2.1.1](#).

Another supporting endpoint will also be defined, in which exacerbations associated with hospitalisations and ER visits that are adjudicated not to be asthma related are removed, and in which hospitalisations and ER visits that are adjudicated to be asthma related are added.

The derivation details for this endpoint are similar to those in [Section 3.2.1.1](#). Any events which are adjudicated with an “undetermined” outcome will be categorised as asthma related when the investigator has judged the event as an asthma exacerbation, and as non-asthma related when the investigator has judged the event not to be an asthma exacerbation.

An annualised rate of exacerbations associated with hospitalisation only will also be derived (also a subset of the primary endpoint defined in [Section 3.2.1.1](#), specifically the 3rd bullet only).

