8.4.7 Independent Adjudication Committee

An independent adjudication committee will be constituted to provide an external independent assessment of blinded data during the Phase 3 trials to confirm the diagnosis of MACE events and investigator reported malignancies that occur from randomization until the end of follow up period.

This independent adjudication committee, will also evaluate cases of ER or urgent care visits and hospitalizations that occur from randomization up to the end of treatment period, as well as all deaths from randomization until the end of follow up period to evaluate whether any such event is due to a worsening of asthma. The committee will include specialists in pulmonology, cardiology, neurology and oncology and will operate in accordance with the Adjudication Committee Charter/Manual of Operations.

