For the purpose of showing consistency of treatment effect across continuous baseline biomarkers (including, but not necessarily limited to, baseline eosinophils, FENO and total IgE), the AAER will be modelled across the continuous biomarker using methods such as moving average or smoothing splines.

For the purpose of showing consistency of treatment effect across categorical baseline or demographic variables (including, but not necessarily limited to, high and low eosinophil categories, high and low FENO categories, specific IgE status, age categories, gender, race, history of exacerbations, asthma controller therapy at randomization, and medium/high ICS dose), a similar model will be fitted as for the primary analysis with additional factors for the relevant subgroup variable and its interaction with treatment. This includes the analysis of AAER in subjects with baseline eosinophils $< 300/\mu\text{L}$ specified in Section 9.4.1.

Any further subgroup analyses, and exact definition of all relevant categories where needed, will be pre-specified in the SAP.

Sensitivity analyses on the primary endpoint will be performed, and will be fully specified in the SAP. These may include, but not necessarily be limited to:

- Analysis which makes provision for data to be missing-not-at-random (MNAR) and which makes different assumptions regarding those subjects who discontinue treatment or study prior to 52 weeks
- Analysis which uses the exacerbation data captured whilst receiving study treatment only
- Analysis in which adjudication outcome of the ER or urgent care visits, hospitalizations and all deaths are considered.

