If the subject attended Visit 17/EOT Week 52 (expected to be the majority of subjects), then:

$$\text{Time at risk (days)} = [\text{earliest (Date of Visit 17; date of last exacerbation assessment status from the eCRF)} - \text{date of randomisation}] + 1$$

Otherwise, if no Visit 17/EOT Week 52 is available for a subject:

$$\text{Time at risk (days)} = [\text{earliest (randomisation date} + 364 \text{ days} + 5 \text{ days; date of last exacerbation assessment during planned treatment)} - \text{date of randomisation}] + 1,$$

where:

Date of last exacerbation assessment during planned treatment = Latest of:

1. *the date of last assessment of exacerbation status from the eCRF.*
2. *the date of death*

The number of days the subject experiences a protocol defined exacerbation, including the subsequent 7 days (when a further exacerbation would not be considered as a second exacerbation), will be subtracted from the time at risk defined above for the primary analysis. For example, if a subject has a single exacerbation which lasts 4 days then $7 + 4 = 11$ days will be subtracted from the time at risk.

It should be noted that the date of last assessment of exacerbation status from the eCRF might be later than the last available visit during the planned treatment period, in the case that the subject remained in the study with incomplete follow-up options after early discontinuation of IP.

For the primary analysis (planned treatment), exacerbations that occur after a subject has discontinued IP but before the end of the time at risk will still be accounted when deriving the total number of exacerbations. Likewise, the time at risk will reflect the time at risk regardless of whether the subject is still on IP or not.

Any exacerbations that starts within the time at risk but ends after this time point will be included in analyses with the end date adjusted to be no later than the time at risk. Any exacerbation that starts after this time will not be included in analyses.

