4.2.4.4 Supporting analyses

Annualised rates for those exacerbations due to ER visits or hospitalisations (a subset of the primary endpoint defined in [Section 3.2.1.1](#), specifically the 2nd and 3rd bullets only) will be summarised descriptively and analysed using a similar model as for the primary analysis.

Annualised exacerbation rates which consider adjudicated outcomes (see [Section 3.2.3.1](#) for details) will also be analysed similarly to the primary analysis. The analysis which considers adjudicated outcomes will also be performed for the exacerbations due to ER visits or hospitalisations and exacerbations due to hospitalisations.

Annualised rate for those exacerbations due to hospitalisations only (a subset of the primary endpoint defined in [Section 3.2.1.1](#), specifically the 3rd bullet only) will be summarised descriptively and analysed using a similar model as for the primary analysis.

These supporting analyses will be performed using the treatment policy strategy only.

Analysis of the time to first exacerbation is described in [Section 4.2.6](#), since this is defined as a secondary endpoint.

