In these summaries, the exposure-adjusted rate will be defined for each treatment as the number of subjects in that treatment group reporting the AE divided by the total time at risk for all subjects in that treatment group, the latter as defined in [Section 3.3.2](#). Rates will be reported as events per 100 subject-years.

Events confirmed by the independent adjudication committee (major adverse cardiac events (MACE) and malignancies) will be summarised by treatment.

The following AE summaries will be produced by treatment group and age category (adults (≥ 65), adults (≥ 18 to < 65) and adolescents (≥ 12 to < 18)):

- Overall summary table as described above, for the on-treatment and on-study periods.
- The most common AEs (defined as those occurring in >3% of subjects in either treatment group), by PT, for the on-treatment and on-study periods.
- AEs summarised by SOC and PT, for the on-treatment and on-study periods.
- SAEs summarised by SOC and PT, for the on-treatment and on-study periods.
- AEs summarised by PT and maximum intensity.

- DAEs summarised by SOC and PT.

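### The SAP's adjudicated exacerbation rate leaves out deaths adjudicated as due to asthma, and its time-at-risk rule can count unassessed days before a death as event-free

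*SAP*

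**What the plan says.** **Protocol.** Section 8.4.7 has the committee assess "all deaths from randomization until the end of follow up period to evaluate whether any such event is due to a worsening of asthma". Section 9.4.3.1 introduces its list of sensitivity analyses for the primary endpoint with "These may include, but not necessarily be limited to". One item on that list is "Analysis in which adjudication outcome of the ER or urgent care visits, hospitalizations and all deaths are considered".

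**SAP, use of adjudication.** Section 3.2.3.1 states that "the primary endpoint does not consider adjudicated outcomes at all". It then defines a supporting endpoint that removes hospitalisations and ER visits judged unrelated to asthma and "in which hospitalisations and ER visits that are adjudicated to be asthma related are added". Section 4.2.4.4 analyses "Annualised exacerbation rates which consider adjudicated outcomes" and refers back to 3.2.3.1 for the definition. In the safety part, 4.2.8.1 says: "Events confirmed by the independent adjudication committee (major adverse cardiac events (MACE) and malignancies) will be summarised by treatment". Appendix 8.4 adds only the adjudicated relationship to COVID-19.

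**SAP, time at risk.** Under 3.2.1.1, a subject without Visit 17 is at risk until the last exacerbation assessment, but no later than randomisation plus 364 plus 5 days. That last assessment is defined as the later of two dates: the last exacerbation status on the eCRF, and "the date of death". Appendix 8.4 repeats the rule for the COVID-19 analysis, with an additional cut-off.

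**The concern.** The asthma judgement on deaths is collected for every subject, but no SAP rate uses it. The protocol's optional analysis names three kinds of adjudicated event, and the SAP's version covers hospitalisations and ER visits. Section 1 of the SAP says that changes from the protocol will be described in Section 6. Section 6 explains the removal of urgent care visits but says nothing about deaths.

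The adjudicated rate is where a reader would expect an asthma death to be counted. As written, a subject who dies of asthma without first meeting an exacerbation criterion contributes follow-up time and no event for the fatal episode.

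The date rule is a separate matter and does touch the primary analysis. It can credit days on which nobody established whether an exacerbation had occurred. Time to first exacerbation is affected in the same way, because its censoring date refers to the same definition.

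**Working it through.** **1. Does any SAP rule count an asthma death as an event?**

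| Place | What it does with a death |
|---|---|
| SAP 3.2.1.1, definition | Three routes: at least 3 days of systemic steroids (or one depot dose), an ER or urgent care visit needing them, or hospitalisation. Death is not a route. |
| SAP 3.2.3.1 and 4.2.4.4 | Adds or removes hospitalisations and ER visits only. |
| SAP 4.2.4.2, Table 7 | Imputes time after a tezepelumab death at the placebo rate, whatever the cause. The fatal episode is not counted. |
| SAP 3.2.4.1, exacerbation-free proportion | Non-completion is a failure, whatever the cause. |
| SAP 4.2.8.1 | Fatal adverse events are tabulated. Adjudicated summaries cover MACE and malignancy. |

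None uses the adjudicated asthma cause.

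**2. Worked case.** A fatal attack at home on study day 180, meeting none of the three criteria and with no earlier exacerbation, gives 0 events and 180 / 365.25 = 0.493 years at risk. The result is the same in the primary and the adjudicated analysis.

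**3. The plan's own figures.** Inputs from Protocol 9.2: 530 per arm, placebo rate 0.9, 50% reduction, dispersion k = 2.4, 10% uniform dropout. Mean follow-up is t = 1 − 0.10 × 0.5 = 0.95 year.

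- Variance of the log rate ratio = (1/n)[(1/t)(1/r0 + 1/r1) + 2k] = (1/530)[(1/0.95)(1/0.9 + 1/0.45) + 4.8] = 0.01568, so SE = 0.1252.
- Power at two-sided 1% = Φ(0.6931/0.1252 − 2.576) = 99.85% (stated: above 99%).
- Minimum detectable reduction = 26.5% (stated: 27%).
- Subgroup power (265 per arm, placebo rate 0.6, two-sided 5%) = 94.5% (stated: 94%).

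The planning model is reproduced, so it can be used for scale.

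**4. Size of the missing event.** Expected events are 530 × 0.95 × 0.9 = 453 on placebo and 530 × 0.95 × 0.45 = 227 on tezepelumab, about 680 in all. The documents give no number of asthma deaths, so 1 to 5 is an assumption.

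| Deaths counted | Rate ratio, all on tezepelumab | Rate ratio, all on placebo |
|---|---|---|
| 0 | 0.500 | 0.500 |
| 1 | 0.502 | 0.499 |
| 3 | 0.507 | 0.497 |
| 5 | 0.511 | 0.495 |

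**5. Size of the date rule.** As an illustration, take a last assessment on day 60 and a death on day 300. The rule credits 300 − 60 = 240 unassessed days, or 240 / 365.25 = 0.657 year. Expected follow-up per arm is 530 × 0.95 = 503.5 years, so the crude rate in that arm falls by about 0.657 / 503.5 = 0.13%. If the subject is on tezepelumab, the rate ratio moves by about 0.500 × 0.0013 = 0.0007.

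**The case against.** Much of the other side's case stands, and it limits the point.

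- **A reader might infer that every asthma death outside hospital is missed.** The documents do not support that. A death preceded by a qualifying steroid course, a depot dose or a qualifying ER or urgent care visit is counted. Exacerbations before the fatal episode also still count. Only deaths meeting none of the three criteria fall through.
- **A reader might infer that unused adjudication distorts the primary endpoint.** It does not. The primary endpoint excludes adjudication by design, and the absence of a fatal event there follows from the exacerbation definition. Assessed days before death are proper risk time for that endpoint.
- **A reader might infer a broken commitment.** The protocol's list is optional, and the SAP does provide an adjudicated analysis. What remains is an unexplained narrowing.
- **A reader might infer that the SAP ignores death.** The fact of death is reflected in Table 7, in the exacerbation-free proportion and in the fatal adverse event tables. Its adjudicated cause is not.
- **The date rule has a limited reach.** It needs a missing Visit 17, it is capped, and it is labelled as applying during planned treatment, a period that SAP 3.1.4 ends at an earlier withdrawal date. A death found after recorded withdrawal should therefore fall outside it. The remaining case is a subject still in the study with sparse contact, such as Option 3 of Protocol 7.1.1. For an ordinary death between visits, the site can often account for the interval.
- **The adjudicated rates are outside the testing hierarchy** of SAP 4.1.2. Counting deaths there cannot change a confirmatory conclusion.

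**Conclusion.** The point holds in a limited form. The adjudicated exacerbation rate omits a fatal asthma attack that meets no exacerbation criterion, although the committee's judgement is available and the protocol named such an analysis as an option. Section 6 should have recorded the narrowing. The no-Visit-17 rule can also count unassessed days as event-free.

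Both effects are small. One extra event shifts the rate ratio by about 0.002 in a supporting analysis, and a 240-day gap for one subject shifts it by about 0.0007 in the primary. These figures rest on the plan's rates and dropout, on crude rates, and on assumed counts of deaths and unassessed days, since the documents give neither. The reason to act is that an analysis built on asthma adjudication should include the most severe asthma outcome.

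**What to change.** 1. **SAP 3.2.3.1, overall adjudicated rate only.** Count a death in the planned treatment period that is adjudicated as due to worsening of asthma as one exacerbation starting on the day of death, unless it falls within an exacerbation already counted or its 7-day window. For these subjects, end time at risk in this analysis at the date of death. Otherwise the event could be lost, because 3.2.1.1 drops exacerbations that start after time at risk ends. Leave the ER/hospitalisation and hospitalisation-only rates as defined, since a death with neither an ER visit nor an admission is not an event of that kind.
2. **SAP 3.2.1.1 and the matching rule in Appendix 8.4.** For the primary analysis, let death end time at risk only when exacerbation status was ascertained up to death. Otherwise use the last assessment date.
3. **SAP Section 6.** Record both changes.

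The cost is some SAP wording and slightly more derivation work, because time at risk will differ between the primary and adjudicated analyses for a few subjects. The adjudication results are already collected. The wording should be settled before unblinding, since a later change would be post hoc.

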3.2.3.2 Other clinic visits pre-BD spirometry

The details of derivation of other clinic visit pre-BD spirometry endpoints are like those in [Section 3.2.2.1](#):

1. Pre-BD FEF_{25-75%}
2. Pre-BD FEV₁/FVC ratio.

3.2.3.3 AQLQ(S)+12 and ACQ-6 responders

Other variables based on AQLQ(S)+12 to be reported at each time point include:

1. AQLQ(S)+12 responder (Yes=1/No=0):
 - Responder: Change from baseline AQLQ(S)+12 total score ≥ 0.5
 - Non-responder: Change from baseline AQLQ(S)+12 total score < 0.5
2. AQLQ(S)+12 response (Improved/No Change/Deterioration):
 - Improvement: Change from baseline AQLQ(S)+12 total score ≥ 0.5
 - No change: $-0.5 < \text{Change from baseline AQLQ(S)+12 total score} < 0.5$
 - Deterioration: Change from baseline AQLQ(S)+12 total score ≤ -0.5 .

Other variables based on ACQ-6 to be reported at each time point include:

1. ACQ-6 responder (Yes=1/No=0):
 - Responder: Change from baseline ACQ-6 score ≤ -0.5
 - Non-responder: Change from baseline ACQ-6 score > -0.5
2. ACQ-6 response (Improved/No Change/Deterioration):
 - Improvement: Change from baseline ACQ-6 score ≤ -0.5
 - No change: $-0.5 < \text{Change from baseline ACQ-6 score} < 0.5$
 - Deterioration: Change from baseline ACQ-6 score ≥ 0.5
3. Subject's asthma control as measured by ACQ-6 score:
 - Well controlled : ACQ-6 score ≤ 0.75
 - Partly controlled : $0.75 < \text{ACQ-6 score} < 1.5$
 - Not well controlled: ACQ-6 score ≥ 1.5 .

In the above, no imputations will be performed for missing values.

3.2.3.4 ACQ-5 and ACQ-7

The ACQ-5 score is the same as ACQ-6 score as defined in [Section 3.2.2.3](#), with the removal of item #6 “daily rescue medication”. An unweighted mean is calculated from the remaining 5 items.

The ACQ-7 score is the same as ACQ-6 score as defined in [Section 3.2.2.3](#), with the addition of an item scored 0-6 for pre-BD FEV₁ % predicted (see below). FEV₁ %predicted will be provided directly (to 2 decimal places) in the spirometry data transfer:

- 0: >95.00%
- 1: 90.00-95.00%
- 2: 80.00-89.99%
- 3: 70.00-79.99%
- 4: 60.00-69.99%
- 5: 50.00-59.99%
- 6: <50.00%

An unweighted mean is calculated from all 7 items.

3.2.3.5 Asthma symptomatic days

The number of asthma symptomatic days will be calculated for each week for each subject as the number of days for which the ASD score (i.e. mean of 10 items) ≥ 1 . The definition of day and week are as given in [Section 3.2.2.4](#).

Change from baseline in the percentage of symptomatic days (out of the number of available days within the week) will be calculated at each post-baseline week. If more than 3 days are missing within any week, this percentage will remain missing for that week.

3.2.3.6 Change from baseline in weekly mean individual ASD items

Individual symptom scores within the ASD will be derived for each subject as follows:

- Severity of wheezing: mean of combined daytime and night-time items. If either the daytime or night-time item is missing, then severity of wheezing is missing.
- Shortness of breath: mean of combined daytime and night-time items. If either the daytime or night-time item is missing, then shortness of breath is missing.
- Severity of cough: mean of combined daytime and night-time items. If either the daytime or night-time item is missing, then severity of cough is missing.
- Severity of chest tightness: mean of combined daytime and night-time items. If either the daytime or night-time item is missing, then severity of chest tightness is missing.

- Frequency of waking (night-time item)
- Limit activities (daytime item).

Weekly means will be calculated similarly to those specified in [Section 3.2.2.4](#).

3.2.3.7 ASD responders

The following will be reported at each time point:

1. ASD responder (Yes=1/No=0):
 - Responder: Change from baseline in weekly mean ASD score ≤ -0.5
 - Non-responder: Change from baseline in weekly mean ASD score > -0.5 .

In the above, no imputations will be performed for missing values.

3.2.4 Other secondary endpoints

3.2.4.1 Other exacerbation endpoints

Time from randomisation to the first asthma exacerbation will also be used as a supportive endpoint to the primary objective, and is calculated as follows:

$$\text{Time to 1}^{\text{st}} \text{ exacerbation (days)} = [\text{Start date of 1}^{\text{st}} \text{ exacerbation} - \text{date of randomisation}] + 1.$$

Subjects without an exacerbation will be censored on the date of last exacerbation assessment, as defined in [Section 3.2.1](#).

Time from randomisation to first asthma exacerbation due to hospitalisations or ER visits will also be calculated, similarly to above.

The proportion of subjects who had no asthma exacerbations during the planned treatment period will also be calculated. A subject will be considered to have completed the planned treatment period, if the planned treatment period is greater than 359 days (Day 364 minus 5, to account for visit windowing).

- Subjects who had no asthma exacerbations during the planned treatment period and who completed the planned treatment period (to Week 52) will be defined as exacerbation free [a].
- Subjects who did not complete the planned treatment period will be defined as not having a successful outcome for this endpoint [b] [c].
- Subjects who did not complete the planned treatment and had an asthma exacerbation will be defined as not having a successful outcome for this endpoint [d].

	No exacerbation	Exacerbation
Completed planned treatment period	[a] Exacerbation free/successful outcome	[d] No successful outcome
Did not complete planned treatment period	[b] No successful outcome	[c] No successful outcome

The proportion will be calculated for each treatment group as:

Number of subjects who were exacerbation free [a] / number of subjects in treatment group.

The proportion of subjects free from exacerbations that required hospitalisation or ER visits during the planned treatment period will also be calculated similarly. A subject who only had an exacerbation which did not lead to hospitalisation or ER visit will be considered a successful outcome for this endpoint.

3.2.4.2 Biomarkers

The effect of tezepelumab on biomarkers will be measured by the change from baseline at each post-baseline time point in:

- Fractional exhaled nitric oxide (clinic visit FENO; note that this is distinct from home-based FENO in [Section 3.2.5.5](#))
- Peripheral blood eosinophils ($10^9/L$ and Cells/ μL)
- Total serum IgE (mg/L and IU/mL)

The definition of baseline is given in [Section 3.1.1](#).

For clinic visit FENO, it is expected that one technically acceptable measurement will be performed at each relevant visit. In the event that more than one technically acceptable FENO measurement is available on the same date at the clinic, all data will be transferred, and the first available technically acceptable FENO measurement on that date will be used. Multiple FENO measurements on different dates will be handled according to the rules for unscheduled/repeat visits (see [Section 3.1.5](#)).

